### 5 Study Design

I-STEP is a single site, unmasked, hybrid type 1 effectiveness-implementation trial which will assess the feasibility, acceptability, and preliminary effectiveness of Brief STAIR and webSTAIR while gathering data on implementation. We will randomize 60 patients (30 in each condition). Participants will complete study survey assessments at baseline (0 weeks), 15 weeks (active treatment), and 9-months post-randomization (follow-up; see Figure 1). To ensure consistency in timing of data collection, assessments are not linked to condition or amount of content completed. We hypothesize that: 1) Brief STAIR and webSTAIR will be effective in reducing PTSD symptoms (primary effectiveness aim) and mental health symptoms (secondary effectiveness aim); 2) Brief STAIR (clinician-administered) will have advantages

over webSTAIR (self-directed) in terms of treatment completion; and 3) webSTAIR will evidence advantages over Brief STAIR in regard to scalability and sustainability. Outcomes will be assessed using survey data and chart extraction.

Self-report measures that have been shown to have excellent psychometric properties will be used to assess mental health and general well-being for each of the three study assessments (baseline, 15 week, and 9-month). This will include the LEC-5 and PCL-5 to assess trauma exposure (historical at the baseline study visit and any new traumatic events at the post-treatment and follow-up assessments) and current PTSD symptoms; the Difficulties in Emotion Regulation Scale (DERS) to assess emotion regulation; the Interpersonal Support Evaluation List (ISEL-12); the Posttraumatic Cognition Inventory (PTCI-9) to assess cognitions associated with PTSD; and the Brief Symptom Inventory (BSI-18) to assess for general mental health issues. Patients will also complete the Coronavirus Stressor Screener, the Everyday Discrimination Scale (EDS), and the Traumatic Symptoms of Discrimination Scale (TSDS) to understand stress response related to Covid-19 and racism. During the baseline assessment, patients will also be asked to complete a demographic questionnaire to collect data on gender, sexual orientation, age, education, marital status, ethnicity, and family income. During the baseline and 15-week assessments, participants will also be asked to complete the Consumer Experiences of Stigma Questionnaire (CESQ) to assess for perceived mental health stigma, the Attitude Toward Seeking Professional Help (ATPHS) to assess attitudes towards help-seeking, and the International Trauma Questionnaire (ITQ) to track their own symptoms. During the 15-week assessment only, participants will be asked to complete the Client Satisfaction Questionnaire (CSQ-8) to assess intervention acceptability. The 15-week assessment also includes an open text box where participants can provide suggestions and recommendations for how to improve STAIR.

Patients may complete the questionnaires over REDCap, in which case the RA will email the participant a participant-specific link to the REDCap surveys using a secure BMC email address. This data will be collected on REDCap with no identifying patient information but the research staff at the clinic will hold the screen ID for eligible and interested patients to link the screening form to the patient. Participants will be given the option to complete the questionnaires in person on paper-and-pencil (depending on COVID-related clinical and research guidance from the institution), or to have them administered verbally (in-person or by phone) by study staff. Regardless of the mode of data collection, study staff will be available to answer any questions that arise. All data will be entered into REDCap.

## 6 Potential Risks and Benefits

### 6.1 Risks

Foreseeable risks or discomforts to subjects as a result of their participation in this study include: a) personal discomfort answering questions about trauma and other psychological symptoms, and b) confidentiality risks.

#### Mitigation of Study Assessment Risks

The risk of discomfort with answering questions about trauma and other psychological symptoms is expected to be short term. To minimize potential discomfort, surveys will be conducted in a private, comfortable setting (or in location of participant's choosing if engaging in telehealth STAIR delivery or

webSTAIR). Participants will be assured that their participation is completely confidential and that neither their name nor any identifying information will be connected with their responses. If the participant feels upset or uncomfortable with any question, they will be free to refuse to answer the question without jeopardizing their study status or any regular clinical treatment received at BMC. They will be informed that they may end their study participation at any time for any reason without negative consequences.

Additionally, all staff will be trained in how to manage distress related to answering questions regarding mental health symptoms, and the study PI is a BMC-credentialed and licensed Clinical Psychologist that can help study staff manage distressed participants. Participants who express severe distress will be referred for evaluation and treatment. If the participant expresses significant distress (but no suicidal or homicidal intent), the PI will make a collaborative plan with the participant in order to address their needs (e.g., brief support, referral, additional phone check ins).

If the participant expresses suicidal or homicidal intent with a plan, standard protocol to assure safety will be followed (i.e., call the IBH clinical social worker on call, send patient to the emergency department, contact BEST). Information obtained from participants will indicate if they are at risk of self-harm. Therefore, we have a suicide safety protocol in place to mitigate this risk. Using the Red Alert function on REDCap, study staff will be automatically notified when a participant indicates they are at risk for suicide (>0 on item 12 of the Brief Symptom Inventory-18 [BSI-19], administered at baseline, 15-week, and 9-month assessments). Study staff will notify the principal investigator and the participants' clinician of the participant's elevated risk for suicide. The principal investigator will evaluate the participant's risk and connect them with appropriate resources and follow-up care (including scheduling a visit with their behavioral health providers in integrated care, referral to other BMC providers, or sending participants to the emergency department if necessary). The treatment follow-up plan will also be communicated to the participant's clinician. If for some reason the participant's safety cannot be assessed, the Boston Emergency Services hotline will be called to evaluate participant safety. In extreme situations, 911 may be called to ensure participant safety.

In the case that suicidality is indicated during the participant's sessions with an IBH clinicians, the IBH clinician will follow the standard safety procedures used in IBH. This process involves clinician assessment of patient safety and negotiating appropriate follow-up care for the patient (including but not limited to: paging the Integrated Behavioral Health team, scheduling a followup visit, referral to outpatient psychiatry, calling the BEST hotline, sending patient to the emergency department). IBH clinicians will report any safety assessments and treatment followup plans related to patients participating in the study to the study team. The suicidality protocol (Psychiatric Emergencies) is the same for all conditions. Specifically, a person could disclose thoughts of harm to self or others in the context of a clinical appointment, through study measures, or during a study visit or check-in with study staff. Participants are not able to disclose this information during webSTAIR sessions because only the user has access to item-level information. We will inform participants in all conditions to reach out to their clinicians, the study team, call 911, and/or present to the ED if they are having a psychiatric emergency.

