data on gender, sexual orientation, age, education, marital status, ethnicity, and family income. During the baseline and 15-week assessments, participants will also be asked to complete the Consumer Experiences of Stigma Questionnaire (CESQ) to assess for perceived symptoms. During the 15-week assessment only, participants will be asked to complete the Client Satisfaction Questionnaire (CSQ-8) to assess intervention acceptability. The 15-week assessment also includes an open text box where participants can provide suggestions and recommendations for how to improve STAIR.

Patients may complete the questionnaires over REDCap, in which case the RA will email the participant a participant-specific link to the REDCap surveys using a secure BMC email address. This data will be collected on REDCap with no identifying patient information but the research staff at the clinic will hold the screen ID for eligible and interested patients to link the screening form to the patient. Participants will be given the option to complete the questionnaires in person on paper-and-pencil (depending on COVID-related clinical and research guidance from the institution), or to have them administered verbally (in-person or by phone) by study staff. Regardless of the mode of data collection, study staff will be available to answer any questions that arise. All data will be entered into REDCap.

*Fidelity to the treatment:*

**For in-person/telehealth STAIR**, patients will be asked to consent to audio-recording of treatment sessions to ensure that fidelity and adherence to the intervention can be evaluated. Research staff will listen to 20% of audio-recorded STAIR sessions and complete a checklist of expected treatment components. Fidelity monitoring will happen in near real-time to assist with therapist training. **For webSTAIR**, study staff will monitor treatment progress via information collected by webSTAIR. This includes behavioral data on module completion, time in each module, total time in program, and the frequency and time spent access each therapy skill. IBH clinicians will also have access to the webSTAIR dashboard so they can monitor their patients' progression through the treatment. The dashboard will be reviewed in consultation meetings.

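### A positive suicide item on a paper questionnaire is not automatically flagged until staff enter it in REDCap; the written step for intent without a plan voiced to study staff also needs clarifying

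*Combined protocol and SAP*

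**What the plan says.** Section 6.1 (Mitigation of Study Assessment Risks) describes how suicide risk in the questionnaires is detected: "Using the Red Alert function on REDCap, study staff will be automatically notified when a participant indicates they are at risk for suicide". The trigger is any score above 0 on BSI-18 item 12, which is asked at baseline, 15 weeks and 9 months. The response follows: "Study staff will notify the principal investigator and the participants' clinician of the participant's elevated risk for suicide". The PI then evaluates the risk and arranges care.

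Not every questionnaire is completed in REDCap. Section 12, like Section 5, allows another route: "Participants will be given the option to complete the questionnaires in person on paper-and-pencil". This depends on institutional COVID guidance. Section 5 adds: "All data will be entered into REDCap". Section 14.1 says that staff may do the entry from paper.

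For what a participant says to study staff, Section 6.1 writes out two branches by level of intent. The lower: "If the participant expresses significant distress (but no suicidal or homicidal intent), the PI will make a collaborative plan with the participant". The upper: "If the participant expresses suicidal or homicidal intent with a plan, standard protocol to assure safety will be followed", meaning the on-call IBH social worker, the emergency department or BEST. Severe distress is referred for evaluation, whatever the intent. The same section states: "The suicidality protocol (Psychiatric Emergencies) is the same for all conditions". It then lists where thoughts of harm to self or others might be disclosed: "in the context of a clinical appointment, through study measures, or during a study visit or check-in with study staff".

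**The concern.** The only detection rule written for item 12 is a software alert, and the alert can act only on what is in REDCap. A paper form completed at an in-person visit is outside it until someone keys the form in. If entry happens later, the alert reaches staff after the participant has gone, although staff were available at the visit and could have acted. Enrolled participants have elevated PTSD symptoms by design (Section 7.1), and adverse events go to the IRB only in summary at continuing review (Section 13.3). Prompt response to suicide risk shown in the study measures therefore depends on Section 6.1.

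The second, smaller matter is the wording of the branches for spoken disclosure. One is limited to no intent, the other to intent with a plan. A research assistant who hears intent without a plan finds no sentence in Section 6.1 that names that case. What is at stake in both parts is participant safety; neither bears on the trial's estimates.

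**Working it through.** No formula applies, and the plan states no figure on this point to reproduce. The check sets the relevant texts side by side.

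**Route of the item 12 answer**

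| How the questionnaire is completed | When the automatic alert can act | Manual check of item 12 written? |
|---|---|---|
| Directly in REDCap | On submission | Not needed |
| Verbally, in person or by phone | On entry by staff, who also hear the answer | No, but staff know the answer at once |
| On paper, in person | Only when staff key the form in | No |

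Sections 5, 12 and 14.1 give no deadline for keying paper forms. Sections 5 and 12 have staff available to answer questions, which is not the same as reviewing the form. On paper, then, the interval between a positive answer and the automatic flag has no written upper limit. This assumes that the alert also fires on records entered by staff; the documents do not say, and if it does not, the gap is wider.

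**What is said to study staff**

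| Level voiced | Text in Section 6.1 |
|---|---|
| Significant distress, no suicidal or homicidal intent | PI makes a collaborative plan |
| Intent without a plan | Not named; severe-distress referral may reach it, and the Psychiatric Emergencies protocol may cover it |
| Intent with a plan | On-call IBH social worker, emergency department, BEST |

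The step that would suit the middle row, notifying the PI and clinician followed by PI evaluation, appears directly after the REDCap alert. Its wording is about suicide risk, and so is item 12. Homicidal intent without a plan is therefore where the written text is thinnest. When suicidality comes up in a session with an IBH clinician, Section 6.1 applies IBH's standard safety procedures and requires no plan, so that route is covered.

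**Size**

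The number of participants affected cannot be estimated. The documents do not give the share of forms on paper, the share scoring above 0 on item 12, or the frequency of spoken disclosure.

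**The case against.** The strongest counter-argument concerns spoken disclosure. Section 6.1 mentions study visits and check-ins immediately after naming the Psychiatric Emergencies protocol, and it speaks there of thoughts of harm to self or others, a lower threshold than intent. In context that puts the study-staff route inside the protocol. The sentences on notifying the PI and clinician follow the alert but are not expressly limited to it, and an earlier sentence refers generally to information obtained from participants. Severe distress is referred whatever the intent. This largely stands. A reader might infer that nobody would act on intent voiced without a plan; the documents do not support that. What remains is a case that the written branches do not name, in a text that leans on a protocol not reproduced here.

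On paper forms, the objection is that completion is in person with staff available, that Section 10 makes REDCap the usual route, and that nothing says forms are left unread. This also stands in part. A reader might infer that paper forms escape the alert altogether, or that positive answers go unseen. Neither follows: all data reach REDCap, and staff may well look at the forms. The supportable statement is that no check is written and the automatic flag waits for entry.

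There is wider cover too: trained staff, a licensed psychologist as PI, the BEST hotline and 911, a therapist on record for each webSTAIR participant (Section 8), and advice to participants to seek help in an emergency. Section 13.2 rates the study as no more than minimal risk. These limit the consequence of a delay but do not bring the reading of item 12 forward to the visit.

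Finally, Sections 2 and 15.3 are partly in the past tense. If follow-up is complete, a change of text cannot help these participants.

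**Conclusion.** The paper-form point holds. As written, a positive suicide item on paper is not automatically flagged until staff enter it, with no stated limit on the delay, and this may be after the participant has left. It rests on two readings: that the REDCap alert is the only detection rule given for item 12, and that no section asks staff to read the item at the visit.

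The spoken-disclosure point holds only as a request for clarification. Intent without a plan is not named between the two written branches, most clearly for homicidal intent, but the Psychiatric Emergencies protocol may already deal with it.

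The frequency of either event is unknown, and no harm or effect on the trial's results is shown. The change is worth making because it is specific and nearly free and concerns safety. Confidence is medium.

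**What to change.** In Section 6.1, beside the description of the alert, add: staff read item 12 on any paper form before the participant leaves, and a score above 0 is handled as a REDCap alert.

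As a secondary clarification, add: any suicidal or homicidal thoughts or intent voiced to study staff, with or without a plan, are passed to the PI and the participant's clinician for evaluation, with the on-call IBH social worker as back-up if the PI cannot be reached. Keep the emergency steps for intent with a plan, and the hotline and 911 fallbacks. If the Psychiatric Emergencies protocol already says this, a citation is enough.

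The cost is one item check per paper form. With 60 participants and 3 assessments, the ceiling is 60 × 3 = 180 checks if every form were on paper; this bounds the workload and does not measure risk. The back-up is already named in Section 6.1, so no new staff are needed. If data collection has ended, carry the wording into the stepped-care work that Section 2 says these findings will inform.

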### **Mitigation of Confidentiality Risk**

Breach of confidentiality is always a concern when participating in a research study. Additionally, the switch to remote data collection due to COVID-19 has created a research standard practice that is

inherently more vulnerable to confidentiality breaches than using paper and pencil. If hospital administration allows research to be conducted in person, we will offer this option to patients. However, we believe that the likelihood of a breach of confidentiality is low given the steps we have put into place to decrease this risk. Specifically, all participant information will be assigned a Study ID and this will be the only way to identify them in the data. Physical study documents with information about participants will be stored in a locked cabinet within a locked office at BMC. Electronic data (e.g., session audio-recordings, webSTAIR data) will be stored on a secure, private, password-protected BMC network server that can only be accessed by members of the study team and will be labeled only with their Study ID.

The webSTAIR site is protected by a data security assurance, ensuring that all content is password-protected, item-level and written content is not viewable outside of an individual account, and all information on the site is maintained in a confidential and secure. Survey data will be stored on REDCap, a HIPAA-compliant, password-protected, access-restricted electronic database. One list of names and Study IDs will be kept on a private, password-protected computer separate from the coded data and accessible only to the study team. Documents with participant information on them (i.e., consent form) will be kept separate from their other data. Any data transmission will take place in pooled form and participants will be identified only by a Study ID. Though therapists will be able to use the STAIR program with all patients, the online program will only be offered to study participants. Training all site staff in using these programs and ensuring that the system runs smoothly for each participant would place a large burden on clinic staff. Furthermore, the program is encrypted to protect the privacy of patients and limit access to the program developers and key study staff. Since site staff cannot support the implementation of the online program without the involvement of study staff, the online program cannot be offered to all patients and will be limited to study participants.

## 6.2 Potential Benefits

There is no direct benefit to participants from taking part in this study. However, patients experiencing symptoms of PTSD may benefit from the findings of the study. Specifically, this study is meant to understand if STAIR is helpful, feasible, and acceptable to patients seen in BMC primary care.

## 6.3 Analysis of Risks in Relation to Benefits

This study advances our ability to assess if PTSD treatment offered in IBH is actually helping reduce mental health outcomes and healthcare utilization as expected and will provide important information from patients about what might need to change in order to be more effectively implemented in this clinic. We believe the risks to participate are reasonable given the importance of direct clinical knowledge that is expected to result from the study.

# 7 Study Subject Selection

## 7.1 Subject Inclusion Criteria

To participate in research components, patients must endorse having experienced an event on the Life Events Checklist for the DSM-5 (LEC-5) and have elevated PTSD symptoms as measured by the PTSD Checklist for the DSM-5 (PCL-5), defined as reporting at least moderate severity of at least one question

1-5 and 6-7 and at least moderate severity on at least two questions 8-14 and 15-20. Additionally, participants must be over 18 years of age, able to engage in therapy in English.

## 7.2 Subject Exclusion Criteria

**Exclusion Criteria:** Participants will be excluded from the study if they (a) do not have reasonable access to the technology needed for both conditions (e.g., phone, computer, internet access), (b) are experiencing bereavement (death of someone close) as primary clinical concern, and is, therefore, not a good fit for a PTSD-specific treatment; (c) are engaged in concurrent cognitive behavioral therapy for PTSD (PE, CPT, or EMDR), or (c) are not appropriate for care in IBH (e.g., need a higher level of care than IBH provides as determined by clinical judgement).

## 8 Study Intervention

### *Clinician-administered Brief STAIR*

Participants randomized to Brief STAIR complete five 30-minute sessions with a study therapist via telemedicine or in-person based on patient preference and Covid-19 restrictions in the setting. Brief STAIR is five sessions and includes all core elements of traditional 10-session STAIR. Each session begins with review of the patients' most recent PCL-5 score (documented in the medical record by the RA). Session 1 provides psychoeducation around the impact of trauma on emotions and relationships, an introduction to the treatment program structure, and a focused breathing exercise. Sessions 2-4 focus on emotion regulation skills across the body, thought, and behavior channels (i.e., the cognitive behavioral therapy triad). These include emotion regulation techniques such as focused breathing and emotion surfing to down-regulate symptoms of over-activation (e.g., anxiety, hyperarousal) and techniques such as behavioral activation and pleasurable activities planning to up-regulate individuals when they are in a depressive or dysthymic state. Session 5 focuses on compassion, strategies for improving social engagement and sustaining relationships (e.g., conflict resolution), review of treatment progress, and a plan to continue use of skills.

